- Section 10.1.1: deletion of non-applicable language for screening failures.
- Section 10.1.5: updates to clarify pharmacokinetic analysis set (PAS) language.
- Section 10.4.1: minor update to list of LDK378 PK parameters that will be derived for PK run-in patients.
- Section 10.4.2.1: Update to non-compartmental method program language. Minor revisions to summary statistics wording.

[REDACTED]

[REDACTED]

[REDACTED]

[REDACTED]

- Section 10.5.2.1: minor changes to endpoint analysis for other secondary objectives.
- Section 10.5.3.2: minor changes to adverse event section to bring clarity and to align with LDK378 program.
- Section 10.8: The timing of primary analysis has been updated to be after all 100 patients completed 24 weeks (6 cycles).
- Section 10.9: [REDACTED]
- Section 10.10: [REDACTED]
- Appendix 14.1: Table title for prohibited concomitant medications requiring caution updated with a notation for LDK378, deletion of CYP2C8 substrates and paclitaxel and updated footnotes for clarification.
- Appendix Table 14-2: list of medication to be used with caution updated and deletion of CYP2B6 and CYP2C8 substrates, addition of simvastatin, removal of clarithromycin and telithromycin.
- Editorial and typographical changes through the document as required.

IRB/IEC

A copy of this amended protocol will be sent to the Institutional Review Board (IRBs)/Independent Ethics Committee (IECs) and Health Authorities.

The changes described in this amended protocol require IRB/IEC approval prior to implementation. In addition, if the changes herein affect the Informed Consent, sites are required to update and submit for approval a revised Informed Consent that takes into account the changes described in this amended protocol.

1 Background

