	
chemotherapy agent and is given for at least 21 days or more. If a cytotoxic chemotherapy regimen was discontinued for a reason other than disease progression and lasted less than 21 days, then this regimen does not count as a prior line of chemotherapy
 
4. Patients must have recovered from all toxicities related to prior anticancer therapies to ≤ 2 (CTCAE v 4.03). The exception to this criterion is for patients with grade 2 nausea/vomiting and/or grade 2 diarrhea despite optimal supportive therapy who will not be allowed to participate in the study. Patients with any grade of alopecia are allowed to enter the study.
 
5. Patients must meet the following laboratory values at the screening visit:
 
 • WBC count $\geq 4.0 \times 10^9 /L$ • Absolute Neutrophil Count $\geq 1.5 \times 10^9 /L$ • Platelets $\geq 100 \times 10^9 /L$ • Hemoglobin (Hgb) $\geq 9 \text{ g/dL}$ • Serum creatinine $< 1.5 \text{ mg/dL}$ and /or calculated creatinine clearance (using Cockcroft-Gault formula) $\geq 30 \text{ mL/min}$ • Total bilirubin $< 1.5 \times \text{ULN}$ except for patients with Gilbert's syndrome who may only be included if total bilirubin $< 3.0 \times \text{ULN}$ or direct bilirubin $< 1.5 \times \text{ULN}$ • Aspartate transaminase (AST) $< 2.5 \times \text{ULN}$, except for patients with liver metastasis, who are only included if AST $< 5 \times \text{ULN}$ • Alanine transaminase (ALT) $< 2.5 \times \text{ULN}$, except for patients with liver metastasis, who are only included if ALT $< 5 \times \text{ULN}$ • Alkaline phosphatase (ALP) $< 5.0 \times \text{ULN}$ 
6. Patient must have the following laboratory values WNL (within normal limits) or corrected to within normal limits with supplements during screening:
 
 • Potassium • Magnesium • Phosphorus • Total calcium (corrected for serum albumin) 
7. Life expectancy ≥ 12 weeks.
 
8. World Health Organization (WHO) performance status 0-2.
 
9. At least one measurable lesion as defined by RECIST 1.1. A previously irradiated site lesion may only be counted as a target lesion if there is clear sign of progression since the irradiation.
 
10. Written informed consent for the main study must be obtained prior to any screening procedures. If consent cannot be expressed in writing, it must be formally documented and witnessed, ideally via an independent trusted witness.
 
11. Willingness and ability to comply with scheduled visits, treatment plans, laboratory tests and other study procedures.

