6.2.4.2 Guidelines for the follow-up of laboratory liver abnormalities

In patients with any clinically relevant laboratory liver abnormality, as defined below, hepatic toxicity monitoring must include ALL of the following liver function tests (LFTs): albumin, ALT, AST, total bilirubin (fractionated if total bilirubin $> 2.0 \times$ ULN), alkaline phosphatase and GGT). Note: for patients with Gilbert Syndrome, total and direct bilirubin must be monitored, but intensified monitoring applies to changes in direct bilirubin only.

In case of any occurrence of ALT/AST/total bilirubin increase to grade 2 the LFTs must be monitored weekly (or more frequently if clinically indicated) until the event resolves to \leq grade 1. Thereafter monitoring must be continued every other week (or more frequently if clinically indicated) for two additional cycles (e.g. 8 weeks). If there is no recurrence of grade 2 ALT/AST/total bilirubin elevations during this period, subsequent monitoring must be performed every 4 weeks.

In case of any occurrence of ALT/AST/total bilirubin increase to grade 3 or 4, LFTs must be monitored weekly (or more frequently if clinically indicated) until the event resolves to \leq grade 1. Thereafter monitoring must be continued every other week (or more frequently if clinically indicated) for four additional cycles (e.g. 16 weeks). If there is no recurrence of \geq grade 2 ALT/AST/total bilirubin elevations during this period, subsequent monitoring must be performed every 4 weeks. For patients with liver metastasis and grade 2 AST/ALT at baseline, increased monitoring is required for grade 3/4 AST/ALT; follow guidelines for grade 3 or 4 AST/ALT.

Patients who discontinue study treatment due to liver toxicity must be monitored weekly (or more frequently if clinically indicated) until the event resolves to \leq grade 1 or stabilization occurs (no CTCAE grade change over 4 weeks). Refer to [Table 6-4](#).

Patients with transaminase increase combined with total bilirubin (TBIL) increase may be indicative of potential DILI, and should be considered as clinically important events.

The threshold for potential DILI may depend on the patient's baseline AST/ALT and TBIL value; patients meeting any of the following criteria will require further follow-up as outlined below:

- For patients with normal ALT and AST and TBIL value at baseline: AST or ALT $> 3.0 \times$ ULN combined with TBIL $> 2.0 \times$ ULN

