- For patients with elevated AST or ALT or TBIL value at baseline: [AST or ALT > 2 x baseline AND > 3.0 x ULN] OR [AST or ALT > 8.0 x ULN], combined with [TBIL > 2 x baseline AND > 2.0 x ULN]

Medical review needs to ensure that liver test elevations are not caused by cholestasis, defined as: ALP elevation > 2.0 x ULN with R value (ALT/ALP in x ULN) < 2 in patients without bone metastasis, or elevation of ALP liver fraction in patients with bone metastasis.

Note: (The R value is calculated by dividing the ALT by the ALP, using multiples of the ULN for both values. It denotes the relative pattern of ALT and/or ALP elevation is due to cholestatic or hepatocellular liver injury).

In the absence of cholestasis, these patients should be immediately discontinued from study drug treatment, and repeat LFT testing as soon as possible, preferably within 48 hours from the awareness of the abnormal results. The evaluation should include laboratory tests, detailed history, physical assessment and the possibility of liver metastasis or new liver lesions, obstructions/compressions, etc.

- Laboratory tests should include ALT, AST, albumin, creatinine kinase, total bilirubin, direct and indirect bilirubin, GGT, prothrombin time (PT)/INR and alkaline phosphatase.
- A detailed history, including relevant information, such as review of ethanol, concomitant medications, herbal remedies, supplement consumption, history of any pre-existing liver conditions or risk factors, should be collected.
- Further testing for acute hepatitis A, B, C or E infection and liver imaging (eg, biliary tract) may be warranted.
- Obtain PK sample, as close as possible to last dose of study drug, if PK analysis is performed in the study.
- Additional testing for other hepatotropic viral infection (CMV, EBV or HSV), autoimmune hepatitis or liver biopsy may be considered as clinically indicated or after consultation with specialist/hepatologist.

All cases confirmed on repeat testing meeting the laboratory criteria defined above, with no other alternative cause for LFT abnormalities identified should be considered as “medically significant”, thus, met the definition of SAE (Section 8.2.1) and reported as SAE using the term “potential drug-induced liver injury”. All events should be followed up with the outcome clearly documented.

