- Hematology: absolute lymphocytes, absolute neutrophils, hemoglobin (anemia), white blood cell (WBC), platelet counts, absolute basophils, absolute eosinophils, absolute monocytes, red blood cells(RBC)
- Biochemistry: alkaline phosphatase (ALP), alanine aminotransferase (ALT), aspartate aminotransferase (AST), total bilirubin, amylase, potassium, sodium, creatinine, glucose(fasting), phosphate, albumin, calcium (corrected for albumin), magnesium, creatinine clearance, direct bilirubin, blood urea nitrogen (BUN) or urea, lipase, Gamma glutamyl transferase (GGT)

For bi-directional parameters, both hyper and hypo summaries will be presented.

- Hormones (males only): Testosterone, LH, FSH, sex hormone binding globulin (SHBG).

In addition, for hematology and biochemistry parameters, a summary table with frequency counts and percentages of patients of new and worsen abnormalities based on CTC grade will be presented.

The following laboratory parameters will be presented in listings and will not be summarized:

- Urinalysis: macroscopic panel (dipstick) (bilirubin, blood, glucose, ketones, WBC, nitrite, pH, protein, specific gravity, urobilinogen), Urinalysis Microscopic panel (RBC, WBC, casts, crystals, bacteria, epithelial cells).
- Coagulation: INR, pro-thrombin time (PT) or Quick Test

The following listings will be produced for the laboratory data for all laboratory parameters where CTC grades are defined:

- Listing of patients with laboratory abnormalities of CTC grade 3 or 4
- Listing of all laboratory data with values flagged to show the corresponding CTC grades and the classifications relative to the laboratory reference ranges.

Liver function tests (LFTs) of interest for LDK378 are total bilirubin (TBIL), ALT, AST and ALP. In what follows, AT refers to ALT or AST values. LFTs will be summarized as follows:

- Shift tables of baseline vs. worst post-baseline on-treatment values for the categories:

- $\text{TBILI} \leq 2 \times \text{ULN}$, $\text{TBILI} > 2 \times \text{ULN}$ and missing TBILI
- $\text{ALT} \leq 3 \times \text{ULN}$, $\text{ALT} > 3 \times \text{ULN}$ and missing ALT
- $\text{AST} \leq 3 \times \text{ULN}$, $\text{AST} > 3 \times \text{ULN}$ and missing AST
- $\text{ALP} < 2 \times \text{ULN}$, $\text{ALP} \geq 2 \times \text{ULN}$ and missing ALP
- Frequency counts and percentages of patients with worst post-baseline on-treatment values in the categories:

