4.1.1 Difference between SAP and protocol

Not applicable.

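### The SAP's combined ALT/AST-plus-bilirubin rows have no baseline condition, although entry admits patients already above one of the cut-offs and the protocol's potential-DILI criterion depends on baseline

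*Protocol*

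**What the plan says.** **Entry.** Inclusion criterion 5 (Protocol summary and Section 5.2) sets AST and ALT below 2.5 x ULN, "except for patients with liver metastasis, who are only included if AST" (and likewise ALT) is below 5 x ULN. Total bilirubin must be below 1.5 x ULN. The Gilbert's exception, "syndrome who may only be included if total bilirubin", allows total bilirubin below 3.0 x ULN or direct bilirubin below 1.5 x ULN. Because of that alternative, 3.0 x ULN is not a strict cap.

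**Protocol 6.2.4.2.** "The threshold for potential DILI may depend on the patient's baseline AST/ALT and TBIL value". With normal baseline values the criterion is AST or ALT > 3 x ULN with total bilirubin > 2 x ULN. The second rule begins "For patients with elevated AST or ALT or TBIL value at baseline". It requires AST or ALT either above both 2 x baseline and 3 x ULN, or above 8 x ULN, together with total bilirubin above both 2 x baseline and 2 x ULN. Cholestasis must be ruled out. In Gilbert's patients the intensified monitoring follows direct bilirubin only.

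**SAP 3.2.9.2.** The liver rows are "Frequency counts and percentages of patients with worst post-baseline on-treatment values in the categories" set by fixed ULN multiples. They include concurrent AT (ALT or AST) > 3 x ULN with TBILI > 2 x ULN, overall and split at ALP 2 x ULN. Concurrent means same date. The section also plans single-parameter shift tables at the same cut-offs, a table of new or worsened CTC grades, and a listing of liver tests for patients above the cut-offs.

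**SAP 4.1.1**, on differences from the protocol: "Not applicable".

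**The concern.** The entry limits overlap the cut-offs of the concurrent rows. A Gilbert's patient can enter already above 2 x ULN for bilirubin, and a liver-metastasis patient already above 3 x ULN for AST/ALT. If that elevation persists, half of the combined pattern was present before the first dose, and the row cannot show it.

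Safety is one of the two primary objectives. Protocol 1.3 describes the pattern in one of these rows (bilirubin > 2, AST/ALT > 3, ALP < 2 x ULN) as hepatotoxicity and gives its frequency as below 1%, so a reader will set the row against that figure. The liver-abnormality table is also among the first interpretable results (SAP 4.5), and the liver shift tables are not. For ECGs the SAP takes the opposite approach: in SAP 3.2.9.3, patients who already met a criterion at baseline leave the denominator for new abnormalities. The liver rows have no counterpart.

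**Working it through.** The plan gives no count or rate for this row, so there is no figure to reproduce. The check applies both rules to patients that inclusion criterion 5 allows.

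**Rules** (all values in x ULN; AT is AST or ALT; a value above 1 is taken as elevated, which is an assumption because 6.2.4.2 gives no cut-off for an elevated baseline)

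- SAP concurrent row: AT > 3 and TBIL > 2 on the same date.
- Protocol 6.2.4.2, normal baseline: the same.
- Protocol 6.2.4.2, any baseline elevation: [(AT > 2 x baseline and AT > 3) or AT > 8] and [TBIL > 2 x baseline and TBIL > 2].

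The cholestasis exclusion and the Gilbert's direct-bilirubin note are left out of this comparison.

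| Case | Baseline AT / TBIL | On treatment AT / TBIL | SAP row | 6.2.4.2 |
|---|---|---|---|---|
| A. Gilbert's, unchanged | 0.8 / 2.8 | 0.8 / 2.8 | no | no |
| B. Liver metastasis, unchanged | 4.5 / 0.8 | 4.5 / 0.8 | no | no |
| C. Both conditions, unchanged | 4.5 / 2.8 | 4.5 / 2.8 | **yes** | no |
| D. Gilbert's, AT rises | 0.8 / 2.8 | 3.5 / 2.8 | **yes** | no |
| E. Liver metastasis, TBIL rises | 4.5 / 0.8 | 4.5 / 2.1 | **yes** | no |
| F. Neither, at entry limit, unchanged | 2.49 / 1.49 | 2.49 / 1.49 | no | no |
| G. Neither, at entry limit, small rises | 2.49 / 1.49 | 3.1 / 2.1 | **yes** | no |
| H. Normal baseline, both rise | 0.8 / 0.8 | 3.5 / 2.1 | yes | yes |

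Why C, D, E and G fail 6.2.4.2:

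- C: AT 4.5 is neither above 2 x 4.5 = 9.0 nor above 8, and TBIL 2.8 is not above 2 x 2.8 = 5.6.
- D: the AT half is met (3.5 > 1.6 and > 3), but TBIL 2.8 is not above 5.6.
- E: the TBIL half is met (2.1 > 1.6 and > 2), but AT 4.5 is above neither 9.0 nor 8.
- G: AT 3.1 is not above 4.98, and TBIL 2.1 is not above 2.98.

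C needs no change on treatment. D and E need a rise in one test only. G starts below both SAP cut-offs and crosses them by small rises, so the two rules also part for patients with neither condition.

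**Size per patient.** The Amendment 3 rationale gives 103 treated patients, which is the Safety Set denominator. 1/103 = 0.97% and 2/103 = 1.94%. At a background below 1%, at most about 0.01 x 103 = 1.03 cases are expected.

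**The case against.** The strongest reply is that the SAP already shows baseline. The shift tables use the same cut-offs and so count patients above each one at baseline. The listing gives all liver values for every patient who can appear in a concurrent row, and with one or two cases a reader can look each up. This stands as far as it goes. However, the shift tables take one test at a time and the listing is not a count, so neither gives the combined pattern by baseline status.

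The second reply is that the figure below 1% in Protocol 1.3 has no baseline condition either, so the existing ALP < 2 x ULN row is the like-for-like comparison. This stands in full, and it is a reason to keep the rows.

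The third is that the baseline-dependent rule can miss real worsening. A liver-metastasis patient going from AT 4.0 to 7.9 and TBIL 0.8 to 5 x ULN is not counted, because 7.9 is above neither 2 x 4.0 = 8.0 nor 8 x ULN. A patient with normal ALT/AST and baseline TBIL 1.2, rising to AT 15 and TBIL 2.3 x ULN, is not counted, because 2.3 is not above 2 x 1.2 = 2.4. This also stands, and it rules out replacing the rows.

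A reader might also infer more than the documents support:

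- *That the SAP reports pre-existing elevations as DILI.* No SAP row carries that label. Protocol 6.2.4.2 keeps the term for SAE reports confirmed on repeat testing with no other cause.
- *That one stable elevation fills a concurrent row.* Cases A and B show that it does not.
- *That SAP 4.1.1 is wrong.* Section 6.2.4.2 is a follow-up guideline. Protocol 10.5.3.3 asks for shift tables and listings and plans no DILI count, so the SAP does not contradict the protocol's analysis section.

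**Conclusion.** The gap is real but narrow. It lies in the concurrent rows, not in the SAP's liver outputs as a whole. As written, those rows merge new combined elevations with ones partly or wholly present before treatment, and no planned output separates the two as a count.

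Each such patient adds 0.97 percentage points, so where about one case is expected, one extra patient could double the row. The total effect cannot be derived. The documents do not give the number of Gilbert's or liver-metastasis patients with elevated baselines, or how often the other test would rise on the same date. A projected number of extra cases would rest on assumed counts alone.

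The table is descriptive and no decision rule depends on it. The reason to act is that it summarises a primary safety objective and the remedy is cheap.

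**What to change.** In SAP 3.2.9.2:

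1. Keep the concurrent rows unchanged as the like-for-like comparison with the figure below 1%.
2. Present each by baseline status: ALT, AST and total bilirubin all normal versus any elevated. State how many patients in each row were already above its AT or TBILI cut-off at baseline.
3. Add one supplementary row applying the laboratory criteria of protocol 6.2.4.2 to all treated patients, including the cholestasis exclusion, and state how the direct-bilirubin note for Gilbert's patients is handled.
4. Report the unadjusted and adjusted rows side by side. Do not rest the safety conclusion on the adjusted row alone.

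The cost is some SAP text, one derived flag and a few table rows, mostly from data already collected. Two items need an explicit rule. Table 7-3 schedules direct bilirubin only when total bilirubin is grade 2 or higher. It also does not list the ALP liver fraction, which 6.2.4.2 uses for cholestasis in patients with bone metastasis. The adjusted row will miss some real worsening in patients with elevated baselines, which is why the unadjusted rows stay.

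Separately, the row of protocol Table 6-3 for AST/ALT with concurrent bilirubin has no baseline condition, while 6.2.4.2 does. The sponsor must reconcile those two passages.

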1.1 Overview of disease pathogenesis, epidemiology and current treatment

1.1.1 Locally advanced or metastatic non-small cell lung cancer (NSCLC)

Lung cancer has been the most common cancer in the world for several decades. In 2008, there were an estimated 1.61 million new cases, representing 12.7% of all new cancers worldwide. It was also the most common cause of death from cancer, with 1.38 million deaths (Ferlay et al 2010). In 2012, an estimated 160,000 deaths were expected in the US (Siegel et al 2012) and 262,000 in the European Union (Malvezzi et al 2012). In China in 2005, there were 497,908 new cases and 428,936 deaths, the highest one among for all malignant tumors (Wu et al 2007). Particularly in males, the highest lung cancer incidence rates are in Central and Eastern Europe (57.0 per 100,000 by age-standardized), Southern Europe (49.0), North America (48.5) and Eastern Asia (45.0). Chinese women have higher lung cancer rates (21.3 cases per 100,000 females) than those in European countries such as Germany (16.4) and Italy (11.4) (Jemal et al 2011).

The World Health Organization (WHO) divides lung cancer into 2 major classes: non-small cell lung cancer (NSCLC) and small cell lung cancer. NSCLC accounts for more than 85% of all lung cancer cases including 2 major types: (1) non-squamous carcinoma (including adenocarcinoma, large-cell carcinoma, other cell types); and (2) squamous cell (epidermoid) carcinoma. Adenocarcinoma (40% of lung cancers) is the most common type of lung cancer seen in the United States and is also the most frequent cell type in nonsmokers (NCCN Guidelines v2. 2014).

Cigarette smoking remains the most important risk factor for lung cancer, although approximately 15% of all lung cancers are diagnosed in patients who never smoked.

The high mortality rate of lung cancer could be explained in an advanced stage for most cases; only 25-30% of new NSCLC cases are diagnosed with localized disease that is potentially curable with surgery (Nguyen et al 2012). The majority of patients are diagnosed with locally advanced or metastatic disease, for which surgery is not indicated.

As summarized in the current National Comprehensive Cancer Network (NCCN) Guidelines for NSCLC, platinum-based combination chemotherapy is superior to best supportive care for patients with advanced, incurable disease (NCCN Guidelines v3. 2012). Platinum-doublet chemotherapy (cisplatin or carboplatin in combination with other chemotherapy agents, with or without bevacizumab) is standard firstline treatment of locally advanced or metastatic NSCLC, unless a patient has a known “druggable” gene mutation or aberration, and is therefore a candidate for a targeted therapy (as discussed below). Although chemotherapy has led to clinical improvements in patients with locally advanced or metastatic NSCLC, the outcome of treatment in the first-line setting remains poor, with median progression-free survival (PFS) and overall survival (OS) of 5-7 months and 10-16 months, respectively (Scagliotti 2008; Ciuleanu 2009; Ettinger 2010; Paz-Ares 2012).

Overall, current treatments are not considered satisfactory for most NSCLC patients and the prognosis continues to be poor despite chemotherapy treatment, with a 5-year OS rate of only 15% (Nguyen et al 2012). In particular, the prognosis for patients presenting with advanced, incurable disease is dismal, with a 5-year OS rate of 3.7% (Howlader et al 2009).

1.1.2 Targeted therapies in NSCLC

During the last few years, improvement in the knowledge of NSCLC biology has led to the identification of molecular events crucial for malignant transformation and cancer cell survival. These aberrant molecular events serve as critical oncogenic drivers for these cancers and, therefore, represent potential therapeutic targets (Gettinger et al 2011). As a result, new targeted treatment options for these patients are evolving. Bevacizumab, a monoclonal antibody directed against vascular endothelial growth factor-A (VEGF-A), and erlotinib, an epidermal growth factor receptor (EGFR) tyrosine kinase inhibitor (TKI), have been approved for the treatment of NSCLC (Gettinger et al 2011).

The case of EGFR TKIs illustrates a new paradigm in the treatment of NSCLC. There is increasing evidence that activating mutations of EGFR define a small subset of patients with NSCLC who have sensitivity to EGFR TKIs (Ettinger et al 2010). Six randomized trials have demonstrated that patients harboring activating EGFR mutations benefit more from EGFR TKIs than from standard chemotherapy in terms of response rate, PFS, toxicity profile and quality of life. In particular, the success of EGFR TKIs highlights the importance of identifying specific NSCLC molecular drivers to appropriately direct targeted agents to specific patient populations.

